7. RATIONALE AND BACKGROUND

Data suggest severe acute respiratory syndrome coronavirus 2 (SARS-CoV-2) likely follows a seasonality pattern as with other respiratory viral infections such as influenza; where activity peaks during the traditional winter viral respiratory season.¹ CDC guidance for the 2020 and 2021 flu seasons included a recommended time interval of at least 14 days between flu and COVID-19 vaccines.² Based on updated data, the CDC has revised their recommendations that COVID-19 vaccines may be co-administered with seasonal influenza vaccines (SIV).³ Specifically, COVID-19 and SIV can be administered concomitantly, and routine administration of all age-appropriate doses of vaccines simultaneously is recommended for children, adolescents, and adults.³ A systematic literature review of 30 studies revealed that when SIV and COVID-19 booster vaccines are combined, there is potential for an increase in the uptake of the COVID-19 vaccine, predominately because many individuals are accustomed to taking SIV annually.⁴

Studies have reported similar safety and immunogenicity among those who received co-administered COVID-19 vaccine and SIV compared to those who received these vaccines separately.⁵⁻¹¹ Three of these studies were clinical trials comparing safety and immunogenicity between SIV and COVID-19 co-administration versus SIV or COVID-19 alone. In these three clinical trials, no safety concerns or immune interferences were found regardless of the vaccines or the age of vaccinated subjects (18-64 or 65+).^{6,9-11} Hause et al in a retrospective cohort study of self-reported vaccine data found a significant increase in reports of systemic reactions 0-7 days following co-administration of a COVID-19 mRNA booster vaccines with an SIV compared to COVID-19 mRNA vaccine alone;⁵ whereas results from a VAERS database⁸ and the National Health Interview Survey⁷ analyses found no unusual or unexpected patterns of AEs or differences in symptom severity.

Regarding efficacy/effectiveness, one study was identified and reviewed. Novavax's NVX-CoV2373 COVID-19 vaccine efficacy when co-administered with the quadrivalent influenza cell-based vaccine Flucelvax (Seqirus UK, Maidenhead) among individuals aged 18 to <65 years was 87.5% (95% CI -0.2 to 98.4); was slightly attenuated compared to when administered alone (89.8% (95% CI 79.7-95.5).⁹

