9. RESEARCH METHODS

9.1. Study Design

[figure not shown]
This structured secondary data collection study will be a retrospective, cohort design to describe concomitant vaccine uptake and subsequent outcomes during one influenza vaccination season. Individuals will be indexed on the date of their first Pfizer-BioNTech mRNA bivalent COVID-19 or influenza vaccine. Exposure groups will be assigned as follows:

- Group 1: Same day (Pfizer-BioNTech mRNA bivalent COVID and flu on the same day);
- Group 2: COVID alone (Pfizer-BioNTech bivalent COVID only);
- Group 3: flu alone (influenza vaccine of any type only).
- CCI

A one year lookback period prior to the index vaccination will be used to identify covariates. Individuals will be followed starting 15 days after vaccination until experiencing one of the following: 1) outcome 2) disenrollment 3) receipt of a second vaccine of the same type 4) receipt of the other vaccine or any type of COVID-19 vaccine 5) end of data or 6) death. Only Pfizer-BioNTech mRNA bivalent COVID-19 vaccine will be assessed. All types of influenza vaccines recommended for the eligible population will be eligible for inclusion, but for the 65+ age group only enhanced influenza vaccines will be included.

PFIZER CONFIDENTIAL

Figure 1. Overall Study Design

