Urinary tract infection	Negative control outcome	≥1 ICD-10-CM diagnosis code in any position/any setting for a urinary tract infection (that occurs >14 days after the patient's first mRNA bivalent COVID-19 or influenza vaccine dose during the study period).
Accidental injury	Negative control outcome	≥1 ICD-10-CM diagnosis code in any position/any setting for accidental injury that occurs >14 days after the patient's first mRNA bivalent COVID-19 or influenza vaccine dose during the study period.
Hospitalization in the 14 days following vaccination (recently vaccinated) Day 1-14	Negative control outcome	
An inpatient (acute facility) claim that meets the following criteria:
 
 1. Occurs ≤14 days after the patient's first mRNA bivalent COVID-19 or influenza vaccine dose during the study period.

PFIZER CONFIDENTIAL

Table 2. Outcome Variables

Variable	Role	Operational definition
		2. Place of service = 21. 3. Non-null confinement ID.
CCI		
CCI		
CCI		
CCI		

PFIZER CONFIDENTIAL

Table 2. Outcome Variables

Variable	Role	Operational definition
		within 60 days following discharge.
CCI [REDACTED]	[REDACTED]	[REDACTED]
Follow-up time	Outcome descriptive	Measured from day 15 through the minimum date of censoring (see follow-up time description in Section 9.3.3). Mean, standard deviation (SD), median (Q1-Q3), minimum, and maximum, will also be summarized for the length of follow-up in each group.

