Prior diabetes	Patient Characteristics	Any code (any setting) within the 1 year baseline for diabetes
Prior kidney disorders	Patient Characteristics	Any code (any setting) within the 1 year baseline for kidney disorders
Month of index date	Patient Characteristics	August/September, October, November, December, January (Note: August will be combined with September as only 1 day of August will be included in the cohort). Model specification: categorical
Prior Influenza vaccination	Patient Characteristics	One claim (NDC or CPT) for influenza vaccine of any type measured between 31 August 2021 – 31 May 2022 Model specification: dichotomous (yes/no)
COVID-19 vaccination in the 1 year prior	Patient Characteristics	One claim (NCD, CPT, procedures) for COVID vaccine of any type in the 365 days before index separated into the following time periods: 
 Recent vaccination: ≤ 60 days prior to index Older vaccination: Between 61 and 365 days prior to index No evidence of vaccination in the prior year If there is evidence of >1 COVID vaccination in the 365 days prior to index, patients are categorized using the date of the most recent dose administered during the baseline period. Model specification: categorical (3 level)
Time from last COVID-19 vaccine dose (Due to the likelihood of misclassification, this variable will be used for descriptive table only, not for model)	Patient Characteristics	Number of days from last COVID-19 vaccine dose. Reported as categories: ^{17,18} <60 days, 60-179, ≥ 180 , not applicable. Continuous statistics including mean, standard deviation (SD), median (Q1-Q3), minimum, and maximum, among those with a prior dose.
Monovalent mRNA COVID-19 vaccine in the 60 days prior to index (Note for descriptive table only, not for model due to collinearity with covid vaccine in the prior year above)	Patient Characteristics	Yes/No. One claim (NCD, CPT, procedures) for monovalent mRNA COVID-19 vaccine between 01 July 2022 – 30 August 2022

PFIZER CONFIDENTIAL

Table 4. Covariates

Variable	Role	Operational definition

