9.7. Data Analysis

There is not a separate Statistical Analysis Plan document for this study. All methodology for summary and statistical analyses of data collected in this study is contained in this section. All computations and generation of tables will be performed using Statistical Analysis System (SAS) version 9.4 or higher (SAS Institute, Cary, NC, US).

All analyses will be conducted for the following age subgroups: 18-64 and 65+.

Descriptive statistics will be presented to describe baseline characteristics by vaccination exposure group. Baseline characteristics will be described by frequency distribution for categorical variables while continuous variables expressed in terms of their mean and standard deviation or median and interquartile range (IQR) as appropriate. In general, missing or unavailable data will not be imputed and data will be analyzed as they are recorded in the database.

To account for imbalance in patient characteristics between the vaccine exposure groups, 2 separate logistic regression models will be used to create a propensity score used to calculate an inverse probability of treatment weights (IPTW). The two models will be as follows: Same day vs COVID-19 alone, and separately Same day vs Flu alone. Weights will be stabilized to avoid exertion of outliers, and we will further evaluate whether there is a need to truncate at the 1st and 99th percentile. Covariate balance before and after weighting will be assessed using standardized mean differences, separately for the same day/COVID-19 alone and Same day/flu alone comparisons. All variables listed in “[Covariates](#)” section with model specification instructions will be included in the score. If there are model convergence issues, changes in model specification may occur (eg, dropping variables with very low prevalence, categories may be collapsed further etc). Variables with residual imbalance will be included in the model for further adjustment.

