Each outcome will be assessed separately. Experiencing one disease specific outcome is not a censoring criteria for the other disease (ie, having a COVID-19 outpatient diagnosis is not a censoring event for the influenza endpoints). Weighted cumulative incidence curves will be used to describe the occurrence of each outcome separately over the entire follow-up period. Given the relatively short follow-up time, we expect small numbers of deaths. Therefore, regular Cox proportional hazards models will be used to estimate HRs and 95% CI for each outcome separately. If we find that death is more common than anticipated, we will consider using Fine and Gray's proportional subdistribution hazards models to account for the competing risk of death. Models for the following vaccine group/outcome combinations will be assessed:

- Same day/COVID-19 only:
 - All-cause hospitalization, composite COVID-19 hospitalization/ED/UC (any position), COVID-19 hospitalization (any position, primary position), COVID-19 ED/UC, COVID-19 outpatient
- Same day/Flu only:
 - All-cause hospitalization, composite flu-hospitalization/ED/UC (any position), flu-hospitalization (any position, primary position), flu ED/UC, flu outpatient.

CCI

Sensitivity Analysis

For disease specific endpoints, we will conduct a sensitivity analysis whereby an additional censoring criteria will be applied. For COVID-19 specific endpoints, we will censor for Paxlovid dispensing. For influenza specific endpoints, we will censor for any of the following influenza treatment dispensing (Oseltamivir phosphate, Zanamivir, Peramivir, Baloxavir marboxil).

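### Calendar time is controlled only by a five-category index month, so the pooled hazard ratios can carry residual seasonal confounding that index-week stratification would remove at little cost

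*Combined protocol and SAP*

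**What the plan says.** Section 9.3.4 (Table 4) records the index date as month in five categories: "August/September, October, November, December, January". The one August day is pooled with September. Under section 9.7 every covariate in that "section with model specification instructions will be included in the score", so month acts through the weights. It reaches the outcome model only through the rule that "Variables with residual imbalance will be included in the model for further adjustment". Balance is judged as follows: "Covariate balance before and after weighting will be assessed using standardized mean differences". Neither index day nor index week is among the covariates.

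For the outcomes, "regular Cox proportional hazards models will be used to estimate HRs and 95% CI for each outcome separately". No time axis, stratification or calendar term is named. Section 9.1 says "Individuals will be followed starting 15 days after vaccination until experiencing one of the following", and Table 2 describes follow-up time as "Measured from day 15 through the minimum date of censoring". Time since index is therefore the natural reading, though it is not stated.

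Tables 1 and 3 censor the single-vaccine groups when the other vaccine is received. The same-day group has already had both, so that event cannot occur in it. The sensitivity analyses in section 9.7 only add censoring at antiviral dispensing, and section 9.9 does not list calendar timing as a limitation.

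**The concern.** Section 7 says of these viruses that "activity peaks during the traditional winter viral respiratory season". Indexing runs from 31 August to 30 January and follow-up ends on 14 February, so both cross that season. Patients indexed on 1 and 30 November share a covariate value and, on a time-since-index axis, a risk set, yet they are compared four weeks apart in the season.

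Two routes can turn this into a distorted HR.

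- **Index dates within month.** Weighting on month equalises month shares but not the days within them. Equal timing should not be taken for granted in the August/September bin: indexing opens on the bivalent vaccine's authorization date, while influenza vaccine was already in use (exclusion criterion 3 concerns doses from 1 to 30 August).
- **Censoring at the other vaccine.** It thins only the comparator. If it clusters in autumn, the groups' risk sets drift apart in calendar date even when index dates are identical.

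Standardized differences on month are blind to both routes. The negative controls (urinary tract infection, injury, hospitalization in days 1-14) need not follow the COVID-19 or influenza waves, so they need not reveal it either. A larger sample does not shrink such a bias.

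**Working it through.** **1. The plan's own figures (section 9.5, age 65+).** Inputs: margin 1.15, one-sided alpha 0.025, power 80%, expected HR 1, Group 1 share p of 63% (COVID-19) or 23% (influenza). Events = (1.960 + 0.842)² / [p(1−p)(ln 1.15)²].
- COVID-19 composite: 7.849 / (0.2331 × 0.01953) = 1,724, as stated.
- Influenza composite: 7.849 / (0.1771 × 0.01953) = 2,269, as stated.

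**2. Null calculation for the pooled HR.** From the documents: index window, entry at day 15, end on 14 February, the values of p. True HR is 1. Let f_g(d) be group g's index-date distribution, with identical month shares in both groups, and h(c) the hazard on calendar day c. At time u since index, over dates d with d+u no later than 14 February, R_g(u) = Σ f_g(d) and E_g(u) = Σ f_g(d)h(d+u). The Cox estimate θ solves

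Σ_u { pE₁ − [pE₁ + (1−p)E₀] × θpR₁ / [θpR₁ + (1−p)R₀] } = 0.

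Assumed, not in the documents: Gaussian waves (influenza peak 5 December, SD 18 days; COVID-19 peak 5 January, SD 24 days), baseline 2% of wave height, exponential tilting of index dates within month, and the month mixes below. Group 1 is earlier by 3 / 5 / 7 days in every month.

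| Index shares Sep/Oct/Nov/Dec/Jan (%) | Influenza HR | COVID-19 HR |
|---|---|---|
| 25/45/20/7/3 | 1.011 / 1.019 / 1.027 | 0.977 / 0.962 / 0.947 |
| 45/38/12/4/1 | 1.006 / 1.009 / 1.014 | 0.976 / 0.960 / 0.944 |
| 20 each | 1.007 / 1.012 / 1.017 | 0.988 / 0.980 / 0.972 |

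If Group 1 is later, the signs reverse (influenza 0.975-0.995, COVID-19 1.012-1.058). No shift, or a flat hazard, gives 1.000. Raising the baseline to 50% of wave height roughly halves the departures.

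Other assumed shapes change the split between the diseases. With a September share of 15-45% and a COVID-19 wave of 2-4 times baseline, a 7-day shift gives 1.010-1.026 for COVID-19. An influenza wave peaking in late November (SD 14) with 15% indexed in September gives 0.937. A shift of 5-10 days confined to September gives only 1.000-1.014.

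**3. Censoring route.** Index dates identical; comparator censored at the other vaccine with a rate peaking on 15 October (SD 20 days, assumed), removing 4-21% under front-loaded month mixes. Null HR: 1.00-1.04 for influenza, 0.98-1.00 for COVID-19.

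**4. Remedies in the same scenarios.** Stratifying by index week returned 0.999-1.001 throughout, and a calendar-date axis with delayed entry returned 1.000. Stratifying by index month does not suffice: in the first mix with a 7-day shift, influenza moves from 1.027 to 1.053 and COVID-19 only from 0.947 to 0.968.

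**5. Meaning against 1.15.** At 1,724 events, SE(ln HR) = 1/√(1,724 × 0.2331) = 0.0499.
- Bias 0.97: one-sided error at the margin = Φ(−1.960 − ln 0.97/0.0499) = 0.089 instead of 0.025.
- Bias 1.03: power = Φ[(ln 1.15 − ln 1.03)/0.0499 − 1.960] = 60% instead of 80%.
- With Table 5 numbers, (382,806 + 225,842) × 0.0056 = 3,408 events: the error becomes 0.135, or power falls from 98% to 87%.

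These error rates ignore any variance inflation from weighting.

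**The case against.** The plan deals with the main part of the problem. Month is in the score, its balance is checked, and it enters the outcome model if imbalance remains. Only the within-month part and the censoring drift are left. This stands, and it is why the point is a refinement.

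The bias is not shown. The documents contain no index-date distribution by group and no rate of later receipt of the other vaccine. A reader might infer that the HR is biased; the documents support only that it can be, and they do not exclude that the groups share the same timing. Nor does every timing difference matter, since a flat hazard gives no bias.

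A reader might also look at late index months alone, where comparable assumptions give null influenza HRs of 1.10 to 1.42, and set those beside the margin. The plan fits no model by index month. Section 9.7 has one weighted model per comparison and outcome in each age group, pooled over months, so those values do not describe any planned estimate.

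Finally, the 1.15 margin belongs to the study-size section. Section 9.7 plans HRs with 95% CIs and states no non-inferiority test, so the error and power figures apply only if results are read against that margin.

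**Conclusion.** The gap is real and small: a cheap improvement, not a defect that undermines the study. Calendar time is controlled coarsely, the time axis is implied, and nothing planned would reveal a residual timing difference. Under the main assumptions, with shifts of 3 to 7 days, the pooled null HR is off by about 1-2% for influenza (just under 3% in the least favourable mix) and 1-6% for COVID-19. Direction depends on which group is later and where the wave falls. Influenza reaches about 6% under one alternative wave. The index-date route contributes nothing without a within-month shift; the censoring route needs none, but does need censoring that clusters in calendar time. Wave shapes, month mixes, shifts and censoring rates are all assumptions. All-cause hospitalization was not modelled, and its seasonality may be weaker.

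**What to change.** In Table 4, replace index month with index calendar week in the propensity model. In section 9.7, stratify the weighted Cox model by index week, collapsing sparse late weeks. Within a week stratum, patients are matched to within a few days on calendar date as well as on time since vaccination. The alternative is calendar date as the time axis with entry delayed to day 15; this matches calendar date but not time since vaccination. Month strata should not be used as a substitute. State the chosen time axis, and report the distribution of index dates within month by group so that readers can see whether the issue arose.

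The cost is one recoded covariate, one stratification term and one descriptive table. The smallest group in Table 5 has 144,695 patients, so weekly strata should be feasible. The downside is a slight loss of information in sparse December-January weeks.

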9.3.4. Covariates

Table 4. Covariates		
Variable	Role	Operational definition
Age	Patient Characteristics, Subgroup	
The number of years between the index date and the patient birth year. Age will be reported in the following categories: 18-64 and 65+.
 
Continuous statistics including mean, standard deviation (SD), median (Q1-Q3), minimum, and maximum, will also be summarized.
 
Model specification: continuous linear

Sex	Patient Characteristics	
Sex will be reported as Male ('M'), Female ('F'), and Unknown
 
Model specification: categorical

US Geographic Region	Patient Characteristics	
US geographic region will be derived from the patient state and categorized into the following:
 
Northeast – Connecticut, Maine, Massachusetts, New Hampshire, Rhode Island, Vermont, New Jersey, New York, Pennsylvania
 
Midwest – Indiana, Illinois, Michigan, Ohio, Wisconsin, Iowa, Kansas, Minnesota, Missouri, Nebraska, North Dakota, South Dakota
 
South – Delaware, District of Columbia, Florida, Georgia, Maryland, North Carolina, South Carolina, Virginia, West Virginia, Alabama, Kentucky, Mississippi, Tennessee, Arkansas, Louisiana, Oklahoma, Texas
 
West – Arizona, Colorado, Idaho, New Mexico, Montana, Utah, Nevada, Wyoming, Alaska, California, Hawaii, Oregon, Washington
 
Other/unknown – Puerto Rico/unknown region
 
Model specification: categorical

Charleston Comorbidity Index (CCI)	Patient Characteristics	
Charleston Comorbidity Index score will be measured during the 12 month baseline period before index and will be reported in the following categories: 0, 1, and 2+. Continuous statistics including mean, standard deviation (SD), median (Q1-Q3), minimum, and maximum, will also be summarized.
 
Model specification: categorical (0,1,2+)

Prior Pneumonia or respiratory failure	Patient Characteristics	Any code (any setting) within the 1 year baseline for any type of pneumonia or respiratory failure
Prior heart disease	Patient Characteristics	Any code (any setting) within the 1 year baseline for heart disease
Prior asthma	Patient Characteristics	Any code (any setting) within the 1 year baseline for asthma

PFIZER CONFIDENTIAL

Table 4. Covariates

Variable	Role	Operational definition
Prior chronic lung disease	Patient Characteristics	Any code (any setting) within the 1 year baseline for chronic lung disease

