Functional status/mobility	Patient Characteristics	A procedure code indicating decreased functional status or mobility in the 365 days prior to index. Model specification: dichotomous (yes/no)
Wellness visit	Patient Characteristics	A CPT or diagnosis code for wellness visit in the 365 days prior to index. Model specification: dichotomous (yes/no)
Immunocompromised status	Patient Characteristics	Assess this group as the following category (Yes/No): ≥ 1 IC condition. Any code within the 1 year baseline for the following conditions: 
 • Hematologic malignancy • HIV/AIDS • Solid organ transplant • Bone marrow transplant • Primary immunodeficiencies • Immunosuppressive medications (eg, chemotherapy, oral corticosteroids ≥ 20mg of prednisone or equivalent for ≥ 14 days). Model specification: dichotomous (yes/no)
Conditions that place or may place patients at risk of Severe COVID-19	Patient Characteristics	Assess this group as the following category (Yes/No): ≥ 1 high risk condition. Baseline comorbid conditions that place or may place

PFIZER CONFIDENTIAL

Table 4. Covariates

Variable	Role	Operational definition
		
patients at risk of Severe COVID-19 will be assessed in the 12 months prior to index date. Conditions will be assessed by having at least 1 ICD-10-CM code in any position in any setting. The conditions include:
 
• Cancer history• Chronic kidney disease (CKD) at any stage• Chronic liver disease• Chronic lung diseases• Dementia or other neurological conditions• Diabetes (type 1 or type 2)• Disabilities; including Down Syndrome• Heart conditions (heart failure; coronary artery disease; or cardiomyopathies)• HIV infection• Hypertension• Immunocompromised state (primary caused by genetic defects; secondary/acquired from prolonged use of corticosteroids or other immune weakening medicines)• Mental health conditions• Overweight and obesity• Physically inactive• Sickle cell disease (SCD) or thalassemia• Smoking; current or former• Solid organ or blood stem cell transplant (includes bone marrow transplants)• Stroke or cerebrovascular disease• Substance use disorders (alcohol; opioid; or cocaine)

PFIZER CONFIDENTIAL

Table 4. Covariates

Variable	Role	Operational definition
		
use disorder)
 
 • Tuberculosis • Pregnancy or recent pregnancy (for at least 42 days following end of pregnancy). 
Model specification: dichotomous (yes/no)

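### Both propensity scores take 21 risk conditions as one at-least-one yes/no term; if that flag is common at 65+, it adjusts weakly for dementia, cancer, stroke, obesity, smoking and others that have no row, and no balance check is specified for them.

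*Combined protocol and SAP*

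**What the plan says.** In section 9.3.4, Table 4, the row for conditions that place patients at risk of severe COVID-19 has 21 bullets. They run from hypertension, overweight and current or former smoking to dementia, stroke and cancer history. On how a bullet counts: "Conditions will be assessed by having at least 1 ICD-10-CM code in any position in any setting". On how the row is used: "Assess this group as the following category (Yes/No): ≥ 1 high risk condition". Its model specification is dichotomous.

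Section 9.7 decides what goes into the two scores (Same day vs COVID-19 alone, Same day vs Flu alone): Table 4 variables from the covariates "section with model specification instructions will be included in the score". On checking: "Covariate balance before and after weighting will be assessed using standardized mean differences". Variables with residual imbalance are then added to the model.

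Three other features of Table 4 matter here.

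- The comorbidity index enters in three levels: 0, 1, 2+.
- An immunocompromised flag, nursing home, skilled nursing facility, functional status ("A procedure code indicating decreased functional status or mobility in the 365 days prior to index") and several utilization counts all carry a model specification, so they are in the score.
- Prior pneumonia or respiratory failure, heart disease, asthma, chronic lung disease, diabetes and kidney disorders have rows of their own but no model specification.

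**The concern.** A flag that is positive for nearly everyone separates few patients. A 70-year-old with controlled hypertension and one with dementia, stroke and cancer have the same value on it. Weighting can balance the flag perfectly while the conditions inside it still differ between groups. If the balance table follows the rows of Table 4, conditions without a row are not tabulated, and the rule to adjust for residual imbalance has nothing to act on.

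The 65+ stratum is where this bites. Section 9.5 finds both composite endpoints adequately sized there and not at 18-64. These conditions plausibly affect both hospitalization and whether two vaccines are given at one visit, and the sizing uses a tight margin of 1.15.

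**Working it through.** **1. What has a term or a row.** Of the 21 bullets, four have a counterpart row (heart conditions, chronic lung disease, diabetes, chronic kidney disease). Three are covered by the immunocompromised row (HIV, immunocompromised state, transplant). That leaves 21 − 4 − 3 = 14 without a row, among them dementia/neurological disease, cancer history, cerebrovascular disease, liver disease, obesity, smoking, mental health, substance use and disability. Cancer is partly reached because the immunocompromised row includes hematologic malignancy and chemotherapy. Under the section 9.7 rule, the six single-condition rows are outside the score because they lack a model specification.

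**2. The plan's own figure.** For the 65+ COVID-19 composite, section 9.5 gives 63% in Group 1, margin 1.15, one-sided alpha 0.025, 80% power and true HR 1. Events = (1.960 + 0.842)² / [0.63 × 0.37 × (ln 1.15)²] = 1,724, as stated. Patients = 1,724 / 0.0056 = 307,857, or 193,950 and 113,907, against the plan's 193,548 and 113,671 (rounding of the event rate).

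**3. Precision available.** Table 5 gives 382,806 + 225,842 = 608,648 patients at 65+. Events = 608,648 × 0.0056 ≈ 3,408. SE of log HR = 1/√(3,408 × 0.63 × 0.37) ≈ 0.0355, before any loss from weighting.

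**4. How much the flag alone removes.** Every carrier of a condition is flag-positive. Let the flag prevalence be F1 and F0 in the two groups and F overall, and the condition prevalence c1 and c0. After weighting on the flag, the condition prevalence becomes c1·F/F1 and c0·F/F0. Example: F1 = 0.90, F0 = 0.92, so F = 0.63 × 0.90 + 0.37 × 0.92 = 0.9074. With c1 = 0.05 and c0 = 0.07, the weighted values are 0.0504 and 0.0690, and the standardized difference goes from −0.084 to −0.079, so 93% remains. All prevalences below are assumed, with condition prevalences of 5 vs 7%, 15 vs 18% and 25 vs 30%:

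| Flag prevalence | Imbalance remaining, flag alone |
|---|---|
| 80 vs 84% | 73-85% |
| 90 vs 92% | 88-93% |
| 95 vs 96% and above | 94-98% |

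**5. Adding the comorbidity index.** A simulation of 1,000,000 patients used assumed 65+ prevalences (for example hypertension 70%, obesity 30%, dementia 8%). It assumed an index counting dementia, stroke, cancer and other major disease, and lower odds of Same day vaccination for carriers of the five conditions below. The flag prevalence came out at 81-98%, depending on how strongly conditions cluster. Weighting on flag plus three-level index left 43-66% of the imbalance for cancer, 61-83% for dementia and stroke, and 62-98% for obesity and smoking. The documents do not list the index components, and the other score terms were not simulated.

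**6. Effect on the hazard ratio.** Bias factor = (1 + p1(RR − 1)) / (1 + p0(RR − 1)), with p1 and p0 the prevalence left after weighting. Both prevalences and RR are assumed. With p1 = 5%:

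| p0 | RR 1.5 | RR 2 | RR 3 |
|---|---|---|---|
| 6% | 0.995 | 0.991 | 0.982 |
| 7% | 0.990 | 0.981 | 0.965 |
| 8% | 0.986 | 0.972 | 0.948 |

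**7. Consequence in each direction.** If Same day patients are healthier, the chance of declaring non-inferiority at a true HR of 1.15 is Φ(−ln b / 0.0355 − 1.96). This gives 4.7% for b = 0.99, 13.5% for 0.97 and 30% for 0.95, against a nominal 2.5%. If they are sicker, the error rate falls (0.24% for b = 1/0.97) and power suffers. At a true HR of 1, power is Φ((ln 1.15 − ln h)/0.0355 − 1.96), where h is the biased HR: 98% at h = 1, 92% at 1.02, 81% at 1.04.

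**The case against.** The strongest reply is that the flag is not the only adjustment. The comorbidity index, immunocompromised status, nursing home, skilled nursing facility, functional status, prior admissions and other utilization terms are all in the score and will absorb part of any imbalance in dementia, cancer or stroke. This stands, and it is why the case is clearest for obesity and smoking. It does not remove the point: the index stops at 2+, and the remaining terms are indirect.

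A reader might infer that the 21 conditions stay largely unbalanced. The documents show neither a baseline imbalance nor the flag's prevalence, so that is not supported. A reader might also infer that the balance check cannot reveal the problem. That goes too far. Heart disease, chronic lung disease, diabetes and kidney disorders have rows and can be checked. The other components are coded anyway to build the flag, so their differences could be reported; the plan just does not specify it. The three negative control outcomes (section 9.3.2) offer a further indirect signal, although they are presented mainly for health-seeking behavior.

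The magnitude is also open to challenge: the leftover gap, the risk ratio and the direction are inputs, not findings. The risk ratio should be conditional on everything else in the score, which argues for the lower end. The 0.95 factor needs both extremes at once. Finally, claims may undercapture smoking and obesity, so separate terms may gain less than hoped.

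**Conclusion.** The point holds in limited form. It is established from the text that 21 conditions enter both scores as one yes/no term, that major conditions have neither a term nor a specified standardized difference, and that six single-condition rows fall outside the score because they lack a model specification. It is conditional that the flag adjusts weakly: this depends on its being common at 65+, with 80-98% assumed. Residual imbalance may therefore go unseen. Its size is illustrative, about 0.5-5% on the HR for a leftover gap of 1-3 points and a conditional risk ratio of 1.5-3. If Same day patients are healthier, false non-inferiority rises above 2.5%; if they are sicker, power falls. The documents do not say which applies. The change is worth making because it closes a possible source of bias at almost no cost.

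**What to change.** In both propensity scores, replace the single flag with separate yes/no terms for the major listed conditions: at least dementia/neurological disease, cancer history, cerebrovascular disease, liver disease, obesity, smoking, mental health, substance use and disability. Give the six existing single-condition rows a dichotomous model specification so that they enter the score. Report a standardized difference for each condition before and after weighting, separately for 18-64 and 65+ and for each comparison. Apply the provision already in section 9.7 for dropping very low-prevalence variables, and keep the flag for the descriptive table.

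The codes are already needed to build the flag, and the smallest comparison has 244,864 + 144,695 = 389,559 patients (Table 5), so the extra terms are easily carried. The cost is a little programming, a longer balance table, and some overlap with the comorbidity index and the immunocompromised term.
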